MI associated with and occurring within 48 h of CABG surgery, with elevation of cardiac biomarker values to $>10 \times$ 99th percentile of the URL in subjects with normal baseline cardiac biomarker values (\leq 99th percentile URL). This classification also requires at least 1 of the following:

- (i) New pathological Q waves, new LBBB on ECG
- (ii) Angiographic new graft or new native coronary artery occlusion
- (iii) Imaging evidence of new loss of viable myocardium or new regional wall motion abnormality.

Acute MI- Symptoms

Presence of acute symptoms of myocardial ischemia, such as chest, upper extremity, mandibular, or epigastric discomfort, or an ischemic equivalent such as dyspnea or fatigue. This is one of the noncardiac marker criteria supporting the diagnosis of acute MI Types 1, 2, 3, 4a, 4b, and 4c.

Acute MI- Acute Ischemic Changes on ECG

Presence of new or presumed new significant ST-segment-T wave (ST-T) changes or new LBBB consistent with acute myocardial ischemia. This is one of the noncardiac marker criteria supporting the diagnosis of acute MI Types 1, 2, 3, and 4.

- Ischemic changes on ECG
In the absence of LVH and LBBB pattern (or other confounder such as a paced rhythm) on ECG, either:
 - a) ST elevation
New (or presumed new) ST elevation at the J point in 2 contiguous leads with the following cut points: ≥ 0.1 mV in all leads other than leads V_2 to V_3 where the following cut points apply: ≥ 0.2 mV in men ≥ 40 y of age; ≥ 0.25 mV in men < 40 y of age, or ≥ 0.15 mV in women; or
 - b) ST depression and T-wave changes
New (or presumed new) horizontal or downsloping ST-segment depression ≥ 0.05 mV in 2 contiguous leads and/or T inversion ≥ 0.1 mV in 2 contiguous leads with prominent R wave or R/S ratio > 1 .
- LBBB
New (or presumed new) LBBB pattern on ECG.

Acute MI- New Q Waves on ECG

Presence of new or presumed new pathological Q waves consistent with MI. This is one of the noncardiac marker criteria supporting the diagnosis of acute MI Types 1, 2, 4, and 5.

New (or presumed new):

- a) Any Q wave in leads V_2 to $V_3 \geq 0.02$ s or QS complex in leads V_2 and V_3
- b) Q wave ≥ 0.03 s and ≥ 0.1 mV deep or QS complex in leads I, II, aVL, aVF, or V_4 to V_6 in any 2 leads of a contiguous lead grouping (I, aVL; V_1 to V_6 ; II, III, aVF)

The same criteria are used for supplemental leads V_7 to V_9 .

Acute MI- Coronary Thrombus Present

Presence of thrombus in a major epicardial vessel consistent with an acute MI. This is one of the noncardiac marker criteria supporting the diagnosis of acute MI Type 1.

- Thrombus on angiography
In the patient with a presumed acute STEMI, the angiographic appearance of thrombus (typically a filling defect) on angiography. This includes the aspiration of thrombus from the infarct vessel before coronary intervention during primary PCI for acute STEMI.
- Thrombus at autopsy
Identification of thrombus in a major epicardial vessel at autopsy.

Acute MI- Change in Noninvasive Imaging

Demonstration of a new change in myocardial viability or function consistent with MI. This is one of the noncardiac marker criteria supporting the diagnosis of acute MI Types 1, 2, 4a, and 5.

- New loss of viable myocardium
Noninvasive imaging evidence of a loss of viable myocardium when compared with the most recent previous noninvasive imaging study.
- New regional wall motion abnormality
Noninvasive imaging evidence of a decrease in regional wall motion contractility compared with the most recent previous noninvasive imaging study.

Acute MI- PCI Angiographic Complication

Occurrence of an adverse angiographic finding during PCI consistent with acute myocardial ischemia. This is one of the noncardiac marker criteria supporting the diagnosis of acute MI Type 4a.

- Loss of major coronary
Angiographic loss of patency of a major epicardial vessel.
- Loss of side branch
Angiographic loss of patency of a side branch.
- Slow flow/no flow/embolization
Angiographic reduction of flow into the coronary microcirculation.

Acute MI- Acute Vessel Occlusion After CABG

Angiographic documentation of a new CABG or new native coronary artery occlusion within 48 h of CABG surgery. This is one of the noncardiac marker criteria supporting the diagnosis of acute MI Type 5.

Prior MI

Presence of any 1 of the following criteria meets the diagnosis for prior MI (before study initiation):

- Pathological Q waves with or without symptoms in the absence of non-ischemic causes
 - a) Any Q wave in leads V_2 to $V_3 \geq 0.02$ s or QS complex in leads V_2 and V_3
 - b) Q wave ≥ 0.03 s and ≥ 0.1 mV deep or QS complex in leads I, II, aVL, aVF, or V_4 to V_6 in any 2 leads of a contiguous lead grouping (I, aVL; V_1 to V_6 ; II, III, aVF)
The same criteria are used for supplemental leads V_7 to V_9
 - c) R wave ≥ 0.04 s in V_1 to V_2 and $R/S \geq 1$ with a concordant positive T wave in the absence of a conduction defect
- Imaging evidence of a region of loss of viable myocardium that is thinned and fails to contract, in the absence of a non-ischemic cause
- Pathological findings of a prior MI

Silent MI

Asymptomatic patients who develop new pathologic Q wave criteria for MI detected during routine ECG follow-up, or reveal evidence of MI by cardiac imaging, that cannot be directly attributed to a coronary revascularization procedure, should be termed 'silent MI'. The diagnosis of a new silent Q wave MI should be confirmed by a repeat ECG with correct lead placement, or by an imaging study, and by focused questioning about potential interim ischemic symptoms.

Stroke [54]

Stroke is defined as an acute episode of focal or global neurological dysfunction caused by brain, spinal cord, or retinal vascular injury as a result of hemorrhage or infarction of sudden onset,

- (a) with persistence of symptoms for ≥ 24 hours or results in death (in < 24 hours) and is not due to an identifiable non-vascular cause (i.e., brain tumor, trauma), or
- (b) with symptoms of short duration (< 24 hours) but evidence of infarction on cerebral imaging.

Stroke will be subclassified into 1 of 3 mutually exclusive categories:

1. Ischemic

An acute episode of focal cerebral, spinal, or retinal dysfunction caused by infarction of central nervous system tissue.

Note: Hemorrhage may be a consequence of ischemic stroke. In this situation, the stroke is an ischemic stroke with hemorrhagic transformation and not a hemorrhagic stroke.

2. Hemorrhagic

An acute episode of focal or global cerebral or spinal dysfunction caused by intraparenchymal, intraventricular or subarachnoid hemorrhage.

Note: Subdural hematomas are intracranial hemorrhagic events and not strokes.

3. Undetermined

An acute episode of focal or global neurological dysfunction caused by presumed brain, spinal cord, or retinal vascular injury as a result of hemorrhage or infarction but with insufficient information (brain image via CT/MRI or autopsy) to allow categorization as either ischemic or hemorrhagic (without documentation or if tests are inconclusive).

As a matter of differentiation, transient ischemic attack (**TIA**) is a transient episode (resolves spontaneously without any evidence of residual deficit < 24 hours) of focal neurological dysfunction caused by brain, spinal cord, or retinal ischemia, without acute infarction. TIAs will not be reported as endpoints but will be reported as an AE.

Recurrent Ischemia with Hospitalization [26]

Recurrent ischemia with hospitalization is defined as ischemic discomfort or equivalent meeting the following criteria:

- (a) lasting ≥ 10 minutes at rest, or repeated episodes at rest lasting ≥ 5 minutes, or an accelerating pattern of ischemic discomfort (episodes that are more frequent, severe, longer in duration, and precipitated by minimal exertion), considered to be myocardial ischemia upon final diagnosis, and
- (b) prompting hospitalization (including an overnight stay on an inpatient unit) within 48 hours of the most recent symptoms, and
- (c) at least 1 of the following additional criteria for coronary artery disease and/or

ischemia:

- new and/or dynamic ST depression ≥ 0.05 mV, ST elevation ≥ 0.1 mV, or symmetric T-wave inversion ≥ 0.2 mV on a resting ECG; or
- definite evidence of ischemia on stress echocardiography, myocardial scintigraphy (e.g., an area of clear reversible ischemia), or ECG-only stress test (e.g., significant dynamic ST shift, horizontal or downsloping); or
- angiographic evidence of epicardial coronary artery stenosis of $\geq 70\%$ diameter reduction and/or evidence for intraluminal arterial thrombus.

If subjects are admitted with suspected myocardial ischemia, and subsequent testing reveals a noncardiac or non-ischemic etiology, this will not be recorded as meeting this end point. Potential ischemic events meeting the criteria for myocardial infarction will not be adjudicated as ischemia requiring hospitalization.

Urgent Coronary Revascularization [26]

Urgent coronary revascularization is defined as ischemic discomfort or equivalent meeting the following criteria:

- (a) lasting ≥ 10 minutes at rest, or repeated episodes at rest lasting ≥ 5 minutes, considered to be myocardial ischemia upon final diagnosis, and
- (b) prompting coronary revascularization during an unscheduled visit to health care facility or during an unplanned (or prolonged) hospitalization for these symptoms or revascularization, which was either done emergently or not previously planned during the course of hospitalization.

Attempted revascularization procedures, even if not successful, will be counted. Potential ischemic events meeting the criteria for myocardial infarction will not be adjudicated as urgent coronary revascularization.

Coronary Stent Thrombosis [56]

All cases of reported death, MI, recurrent ischemia with hospitalization and urgent coronary revascularization will be reviewed and adjudicated with respect to stent thrombosis according to the Academic Research Consortium definition below:

Timing:

Acute stent thrombosis*	0 to 24 hours after stent implantation
Subacute stent thrombosis*	>24 hours to 30 days after stent implantation
Late stent thrombosis†	>30 days to 1 year after stent implantation
Very late stent thrombosis†	>1 year after stent implantation

Stent thrombosis should be reported as a cumulative value over time and at the various individual time points specified below. Time 0 is defined as the time point after the guiding catheter has been removed and the subject has left the catheter laboratory.

*Acute or subacute can also be replaced by the term early stent thrombosis. Early stent

thrombosis (0-30 days)

†Includes primary as well as secondary late stent thrombosis; secondary late stent thrombosis is a stent thrombosis after a target lesion revascularization.

Grading:

Three categories of evidence define the probability that coronary artery stent thrombosis has occurred:

1) Definite stent thrombosis*

a. Angiographic confirmation of stent thrombosis†

The presence of a thrombus‡ that originates in the stent or in the segment 5 mm proximal or distal to the stent and presence of at least 1 of the following criteria within a 48-hour time window:

- Acute onset of ischemic symptoms at rest
- New ischemic ECG changes that suggest acute ischemia
- Typical rise and fall in cardiac biomarkers (refer to definition of spontaneous MI)
- Nonocclusive thrombus
Intracoronary thrombus is defined as a (spheric, ovoid, or irregular) noncalcified filling defect or lucency surrounded by contrast material (on 3 sides or within a coronary stenosis) seen in multiple projections, or persistence of contrast material within the lumen, or a visible embolization of intraluminal material downstream.
- Occlusive thrombus
TIMI 0 or TIMI 1 intrastent or proximal to a stent up to the most adjacent proximal side branch or main branch (if originates from the side branch).

b. Pathological confirmation of stent thrombosis

Evidence of recent thrombus within the stent determined at autopsy or via examination of tissue retrieved following thrombectomy.

2) Probable stent thrombosis

Clinical definition of probable stent thrombosis is considered to have occurred after intracoronary stenting in the following cases:

- Any unexplained death within the first 30 days§
- Irrespective of the time after the index procedure, any MI that is related to documented acute ischemia in the territory of the implanted stent without angiographic confirmation of stent thrombosis and in the absence of any other obvious cause.

3) Possible stent thrombosis

Clinical definition of possible stent thrombosis is considered to have occurred with any unexplained death >30 days after intracoronary stenting.

*Definite stent thrombosis is considered to have occurred by either angiographic or pathological confirmation.

†The incidental angiographic documentation of stent occlusion in the absence of clinical signs

or symptoms is not considered a confirmed stent thrombosis (silent occlusion).

‡Intracoronary thrombus.

§For studies with ST-elevation MI population, one may consider the exclusion of unexplained death within 30 days as evidence of probable stent thrombosis.

When available data support >1 classification, the highest level of certainty should be reported.

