7.2 General Aspects of Statistical Evaluation

Statistical analyses will be performed using SAS version 9.23 and, where appropriate (e.g., specific pharmacokinetic analyses) other validated software. Statistical analyses will be performed in accordance with the study protocol, and a comprehensive Statistical Analysis Plan (SAP) which will be prepared before unmasking of the data. The SAP will provide further details of the analyses and presentation of the data and will contain ground rules and data handling conventions used to perform the analyses. Both the data and the proposed methods of analyses will be reviewed continuously during the study by the study team, which includes input from statistical, clinical and data management personnel. Before database lock, a masked review will take place during which all important protocol deviations will be discussed and agreed by the team and any ambiguities in study outcomes will be adjudicated in a masked fashion by the protocol team.

The primary and secondary outcome measures will be treated as binary outcomes with any individual experiencing the event within the specified time frame after treatment classified as

positive for the outcome and other individuals classified as negative. Details of the measures will be included in the SAP.

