7.6 Efficacy Analyses

Efficacy endpoints are defined in **Appendix B**. Only efficacy endpoint events adjudicated by the CEC will be used in the secondary efficacy analyses.

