Type 2: any overt, actionable sign of hemorrhage (e.g., more bleeding than would be expected for a clinical circumstance, including bleeding found by imaging alone) that does not fit the criteria for type 3, 4, or 5 but does meet at least one of the following criteria: (1) requiring nonsurgical, medical intervention by a healthcare professional, (2) leading to hospitalization or increased level of care, or (3) prompting evaluation

Type 3

Type 3a

Overt bleeding plus hemoglobin drop of 3 to <5 g/dL* (provided hemoglobin drop is related to bleed)

Any transfusion with overt bleeding

Type 3b

Overt bleeding plus hemoglobin drop ≥ 5 g/dL* (provided hemoglobin drop is related to bleed)

Cardiac tamponade

Bleeding requiring surgical intervention for control (excluding dental/nasal/skin/hemorrhoid)

Bleeding requiring intravenous vasoactive agents

Type 3c

Intracranial hemorrhage (does not include microbleeds or hemorrhagic transformation, does include intraspinal)

Subcategories confirmed by autopsy or imaging or lumbar puncture

Intraocular bleed compromising vision

Type 4: CABG-related bleeding

Perioperative intracranial bleeding within 48 h

Reoperation after closure of sternotomy for the purpose of controlling bleeding

Transfusion of ≥ 5 U whole blood or packed red blood cells within a 48-h period†

Chest tube output ≥ 2 L within a 24-h period

Type 5: fatal bleeding

Type 5a

Probable fatal bleeding; no autopsy or imaging confirmation but clinically suspicious

Type 5b

Definite fatal bleeding; overt bleeding or autopsy or imaging confirmation

Platelet transfusions should be recorded and reported but are not included in these definitions until further information is obtained about the relationship to outcomes. If a CABG-related bleed is not adjudicated as at least a type 3 severity event, it will be classified as not a bleeding event. If a bleeding event occurs with a clear temporal relationship to CABG (i.e., within a 48-h time frame) but does not meet type 4 severity criteria, it will be classified as not a bleeding event.

*Corrected for transfusion (1 U packed red blood cells or 1 U whole blood=1 g/dL hemoglobin).

†Cell saver products are not counted.

EFFICACY

Major Adverse Cardiac Event (MACE)

Defined as the composite endpoint of cardiovascular death, non-fatal MI, non-fatal stroke, recurrent ischemia with hospitalization, or urgent coronary revascularization.

Death [53, 54]

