Cardiovascular death is the endpoint defined in this trial (as opposed to all-cause death) and only suspected CV death cases will be submitted for adjudication to the CEC. Death will be classified as cardiovascular, non-cardiovascular, or unknown/undetermined. All deaths will be assumed to be cardiovascular in nature unless a non-cardiovascular cause can be clearly shown, with the exception of death without any additional information, which will be classified as unknown/undetermined.

The primary cause of death is determined by the principal condition that caused the death, not the immediate mode of death, as per the following:

Cardiovascular death:

- **Acute MI**

Death by any cardiovascular mechanism (arrhythmia, sudden death, HF, stroke, pulmonary embolus, PAD) within 30 days after an acute MI, related to the immediate consequences of the MI, such as progressive HF or recalcitrant arrhythmia. There may be assessable (attributable) mechanisms of cardiovascular death during this time period, but for simplicity, if the cardiovascular death occurs within 30 d of an acute MI, it will be considered a death due to MI.

Note: Acute MI should be verified to the extent possible by the diagnostic criteria outlined for acute MI or by autopsy findings showing recent MI or recent coronary thrombosis. Death resulting from a procedure to treat an MI (PCI or CABG), or to treat a complication resulting from an elective coronary procedure to treat myocardial ischemia (i.e., chronic stable angina) or death due to an MI that occurs as a direct consequence of a cardiovascular investigation/procedure/operation should be considered as a death due to a cardiovascular procedure.

- **Sudden cardiac death**

Death that occurs unexpectedly and not within 30 d of an acute MI.

Note: Sudden cardiac death includes the following scenarios:

- Death witnessed and occurring without new or worsening symptoms;
- Death witnessed within 60 min of the onset of new or worsening cardiac symptoms unless the symptoms suggest acute MI;
- Death witnessed and attributed to an identified arrhythmia (e.g., captured on an ECG recording, witnessed on a monitor, or unwitnessed but found on ICD review);
- Death after unsuccessful resuscitation from cardiac arrest (e.g., ICD unresponsive sudden cardiac death, pulseless electrical activity arrest);
- Death after successful resuscitation from cardiac arrest and without identification of a specific cardiac or noncardiac etiology;

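### A stented subject who dies within 30 days with nothing further known is scored as probable stent thrombosis but not as cardiovascular death or MACE

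*Combined protocol and SAP*

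**What the plan says.** Appendix B sets a default for the cause of death: "All deaths will be assumed to be cardiovascular in nature unless a non-cardiovascular cause can be clearly shown". It then makes one exception: "with the exception of death without any additional information, which will be classified as unknown/undetermined". Unknown/undetermined is kept as a third category beside cardiovascular and non-cardiovascular death.

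MACE is "Defined as the composite endpoint of cardiovascular death, non-fatal MI, non-fatal stroke, recurrent ischemia with hospitalization, or urgent coronary revascularization". Unknown/undetermined death is not a component. Section 7.2 makes the secondary outcomes binary: a subject with the event in the time window is "positive for the outcome and other individuals classified as negative". Section 7.6 adds: "Only efficacy endpoint events adjudicated by the CEC will be used in the secondary efficacy analyses".

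Stent thrombosis is a separate secondary endpoint, counted when definite or probable, through 30 and 90 days (Section 6.7.1.4). After stenting, Appendix B includes under probable: "Any unexplained death within the first 30 days". Later deaths fall lower: "Clinical definition of possible stent thrombosis is considered to have occurred with any unexplained death >30 days after intracoronary stenting".

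The routes to the Clinical Events Committee (CEC) also differ. For the death endpoint, "only suspected CV death cases will be submitted for adjudication to the CEC"; for stent thrombosis, the appendix has every reported death reviewed.

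**The concern.** A death about which nothing is known is by definition unexplained. In a stented subject within 30 days, one part of Appendix B attributes that death to a clotted coronary stent, while another part keeps it out of cardiovascular death and so out of MACE. The stent-thrombosis table and the MACE table would then disagree about the same subject.

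MACE is the key secondary endpoint. Section 7.5.4 makes the acceptable bleeding margin depend in part on the efficacy benefit found, and Section 7.6.1 uses these outcomes in the risk/benefit judgement for Phase 3. After the 14-day visit, scheduled contact is by telephone (Sections 6.5.10 and 6.5.11), so a death may be reported with little detail. If the conflict is settled only after unmasking, the choice will be open to challenge.

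**Working it through.** No figure in the plan depends on this rule, so there is none to reproduce. The check is to trace the rules for one subject and then gauge scale.

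**Scoring trace** (death is the subject's only possible event)

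| Subject | CV death | MACE | Definite/probable stent thrombosis |
|---|---|---|---|
| Stented, dies by day 30, no information | negative | negative | **positive** |
| Stented, dies by day 30, unexplained but some information | positive (default) | positive | positive |
| Stented, dies days 31–90, no information | negative | negative | negative (possible only) |
| Not stented, dies at any time, no information | negative | negative | negative |

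Only the first row is inconsistent. In the second row the cardiovascular default applies, or the sudden-cardiac-death category, and the endpoints agree. In the last two rows the endpoints also agree. Whether those deaths should count as MACE is a question of convention, not a conflict between rules.

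**Number of subjects.** The documents give no mortality rate and no share of deaths without information. The following are assumptions, for scale only:

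- 90-day mortality 0.5% to 2%, with 10% to 20% of deaths uninformative: 600 × 0.005 × 0.10 = 0.3, up to 600 × 0.02 × 0.20 = 2.4 subjects. This counts all no-information deaths to day 90.
- Restricted to the first row: take 56% stented (the PCI share in the earlier vorapaxar phase 2 trial, Section 4.1.1, as a stand-in) and assume half of deaths occur by day 30. Then 0.3 × 0.56 × 0.5 = 0.08, up to 2.4 × 0.56 × 0.5 = 0.67 subjects.
- Poisson with mean 0.67: P(0) = exp(−0.672) = 0.51 and P(0 or 1) = 0.51 × (1 + 0.672) = 0.85. Even at the upper end, zero or one subject is the likely count.

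**Effect of one rescored death** (400 on pooled PZ-128, 200 on placebo)

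- Incidence rises by 1/400 = 0.25 points on PZ-128 or 1/200 = 0.5 points on placebo.
- MACE, using that vorapaxar trial's composite rates of 6% and 9% as an illustration: 24/400 against 18/200 is a difference of −3.0 points. One death on PZ-128 gives 25/400 − 18/200 = −2.75. One on placebo gives 24/400 − 19/200 = −3.5.
- CV-death component, assuming 2/400 against 1/200 (0.5% in each arm): one death on PZ-128 gives 0.75% against 0.5%, and one on placebo gives 0.5% against 1.0%. The component is sparse enough for a single death to be visible.

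**The case against.** The strongest reply is that the text does not force inconsistent scoring. Appendix B describes an unknown death as one that cannot be attributed to either a cardiovascular or a non-cardiovascular cause. A committee that has just called a death probable stent thrombosis could reasonably regard it as attributed. Section 9.3.2 gives the CEC further instructions and a charter, and Section 7.2 leaves outcome details to a SAP to be prepared before unmasking. Neither the charter nor that SAP is among the documents. This stands as a possible resolution, but nothing in the text requires it, and the exception for deaths without information is explicit.

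The cases should also be few. Section 6.7.2.2.6 requires every death to be reported within 24 hours, with a full description and any autopsy report, and Sections 6.5.9 to 6.5.11 have sites collect source documents. That also stands. A relative's dated account of the death might already take it outside the exception; the appendix does not say how little information is too little.

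A reader might infer that a dead subject is analysed as free of cardiac events. The documents do not support that as a general statement. The stented subject who dies by day 30 is recorded as a stent thrombosis, a subject with an earlier MACE component stays MACE-positive, and Section 7.5.4 requires a separate listing of deaths. A reader might also infer that unexplained deaths in general drop out of MACE. They do not, because the default makes all but the wholly uninformative ones cardiovascular.

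Finally, Section 7.6.2 also plans Kaplan-Meier and Cox analyses. The negative score applies exactly to the binary analysis. In the time-to-event analysis such a death is still not an event, and its censoring is not stated.

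**Conclusion.** The conflict is real but narrow. It covers only stented subjects with no earlier MACE component who die within 30 days with no information at all. For them, the current text gives probable stent thrombosis on one endpoint and no cardiovascular death and no MACE on two others. The likely number is zero or one, on assumed rates. One such death shifts an arm's incidence by 0.25 or 0.5 points, which is small for MACE but noticeable in a sparse cardiovascular-death component.

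It does not follow that every unknown death must be counted as cardiovascular in the main analysis. The plan prespecifies a convention for those deaths, and the opposite convention is equally debatable. What needs correcting is the disagreement between two rules on the same death.

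Priority is low. The affected endpoints are secondary, Section 7.6.2 treats the efficacy analyses as descriptive, and the primary bleeding endpoint, sample size and margins are untouched.

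**What to change.** Before unmasking, add to Appendix B and the SAP:

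1. Any death adjudicated as definite or probable stent thrombosis counts as cardiovascular death, both in MACE and in its cardiovascular-death component.
2. A sensitivity analysis of MACE and of cardiovascular death counts all remaining unknown/undetermined deaths as cardiovascular.

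The CEC charter should carry the same rule. No new referral path is needed for item 1, because Appendix B already has all reported deaths reviewed for stent thrombosis.

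The cost is a sentence for each item and one extra run of planned analyses, with no added data collection. The downside is that an occasional non-cardiovascular death may be counted as cardiovascular.
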